- C. Identify baseline predictors of responsiveness to each intervention and the mechanistic basis for each treatment. Candidate predictors are (a) demographic variables (e.g., sex, age, race, ethnicity, education); (b) clinical history variables (e.g., FI frequency, volume, duration, and association with urgency and diarrhea); and (c) baseline pelvic floor physiology (e.g., anal canal resting pressure, squeeze pressure, duration of squeeze, rectal sensory threshold for first sensation and urgency, maximum tolerable volume, structural integrity of anal sphincters assessed by ultrasound, and integrity of the pelvic floor innervation by trans-sacral and trans-lumbar magnetic evoked potentials).

- D. Evaluate treatment combinations. Patients who do not meet the responder criterion by 3 months follow up will be offered the option of choosing additional therapy. This constitutes a pragmatic clinical trial which mimics clinical practice and will provide preliminary data for a future study. A second reason for allowing patients to add an additional preferred treatment if they do not show at least a 75% improvement is to facilitate recruitment; in our feasibility survey, subjects told us that the opportunity to try another treatment if the first failed would increase their willingness to be randomized. Data analysis will estimate 95% confidence intervals for the percent of responders to each treatment combination and to each monotherapy, and differences in responder rates between groups will be assessed.
  - Research objective 4. To compare the improvement in FI after combination treatment versus monotherapy and compare improvement among various treatment combinations, up to 24 months after administration of each treatment combination, compared to monotherapy.
  - Research objective 5. To estimate differences in the magnitude of improvement in FI from baseline to end of treatment between the treatment combinations.
- E. Assess the efficacy and durability of enhanced medical treatment and identify patient characteristics that predict treatment response.
  - Research objective 6. To estimate the responder rate during the last two weeks of enhanced medical treatment and also during follow up at 3, 6, 12, and 24 months.
  - Research objective 7. To assess the proportion of patients reporting AEs of pelvic pain of grade II or higher, or SAEs requiring hospitalization, during all weeks of medical treatment.

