2.3. Expected impact of this FI comparative effectiveness trial: The proposed project will improve scientific knowledge, technical capability, and clinical practice as they relate to the treatment of FI. A critical barrier to progress in the treatment of FI is the lack of understanding regarding comparative effectiveness of currently approved treatment modalities and their pathophysiological basis. Our objectives are to address this significant gap in our knowledge by (1) comparing the effectiveness, safety, and cost of two treatments, BIO and INJ at 3, 6, 12, 18, and 24 months following the end of treatment; (2) identifying patient characteristics at baseline that predict response to each intervention; (3) investigating the mechanistic basis for treatment success by examining rectal sensory thresholds, rectal compliance, neurophysiological parameters, and stool consistency; (4) evaluating the response to treatment combinations selected by non-responders compared to the primary treatment assignment; and (5) assessing the rate of response to EMM, the durability of response, and patient characteristics that predict benefit from medical treatment. SNS will not be included as a randomized study treatment as it is a more invasive treatment and appears to negatively impact the willingness of patients to participant in the study. We will offer SNS to participants as an additional treatment choice when they are identified as non-responders to the randomized treatment at the 3-month follow-up assessment, thus allowing them the opportunity to choose as an additional treatment either SNS or the other intervention to which they were not initially randomized (either BIO or INJ). Participants who do not meet clinical criteria for receiving SNS, or who previously received and did not respond to SNS treatment will not be offered SNS as a treatment option at 3-month follow up.

When the aims of this project are achieved, the concepts, methods, technologies and treatments or preventive interventions related to the management of FI will be changed as a result of (1) development of a rational basis for recommending treatment with BIO or INJ; (2) demonstration of comparative effectiveness of each treatment modality; and (3) a new understanding of the effects of each treatment on bowel symptoms, and quality of life, especially regarding safety, tolerability, and adherence.

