  - INJ will include a preparation for treatment and a treatment visit. Preparation will include the use of enemas and minimal restrictions on food intake. Prophylactic antibiotics should be started on the day of the procedure, per the treatment SOP. On the day of the procedure, a physician will inject 1 ml of dextranomer into each of 4 quadrants of the rectum proximal to the dentate line. Ten seconds will be allowed to pass before the injection needle is withdrawn to minimize drainage of the dextranomer. The patient will be scheduled to return in 6 weeks for possible repeat injection of a second 4 ml of dextranomer. At this second appointment, if FI has improved by 75% or more compared to baseline, the patient will be continued without a second injection. However, if the rate of FI is greater than 75% of baseline, the patient will be offered a second injection of dextranomer.
- 4. Combination therapy: The primary assessment of efficacy is at 3 months following the first treatment visit completed, and patients who have not achieved at least a 75% reduction in FI frequency compared to baseline will be classified as treatment failures; they will be invited to choose either the treatment to which they were not randomized or SNS as an adjunctive treatment for the remaining months of the study. One reason for offering non-responders an opportunity to try an additional treatment is to increase the likelihood that patients will consent to be randomized despite possibly having a priori preferences for one of the two treatments. The assumption that this will increase willingness to be enrolled was confirmed in the pilot feasibility survey we performed in 187 patients with FI representing the clinical sites: 57% of patients reported that the ability to receive the treatment of their choice if the assigned treatment was not effective, was important to their willingness to be randomized. Moreover, the estimated 46% of patients who do add a second treatment after the 3 months primary assessment will enable us to collect exploratory data on the possible benefits of combining these treatments. (None of the two investigational treatments can be discontinued.) Thus, the patients

Figure 1. Study Design

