#### 5.4 Estimated patient flow for this study

Figure 3 shows the estimated flow of patients through this study and identifies our assumptions regarding attrition. We estimate we will need to screen 855 patients because 2/3 will be ineligible or unwilling to be randomized. This leaves 285 to be recruited into the EMM protocol. Based on the Heymen study, we assume

15% attrition during this treatment phase and also assume that 20% (n=57) will be responders to EMM and therefore not eligible for randomization. This will leave 194 to be randomized (97 per group).

Figure 3 shows that we expect 78 from the BIO group to complete the 3-month assessment after allowing for attrition of 20% and we expect 92 from the INJ group to complete the 3-month assessment. (We assume attrition will be no greater than 5% for the INJ group because this is a low-burden treatment and also because patients will want to be screened for AEs related to INJ.) However, the statistical analysis will be by intent to treat (ITT) and will include all 194 randomized to treatment; patients who are lost to follow up prior to 3 months will be considered treatment failures. The number of patients we expect to be responders to each of the treatments at the 3-month assessment is based on the pivotal trials shown in Table 1. We separated them in this way in Figure 3 to be able to estimate the numbers of non-responders who are likely to choose an additional treatment option after 3 months. The expected number of non-responders eligible for an additional therapy at 3 months is 63 for the INJ arm^16 and 17 for the biofeedback arm^15. Assuming equal probability of choosing either of the 2 available options as an added or alternative treatment, we could expect 40 patients to choose the SNS treatment, 32 to choose BIO, and 9 to choose INJ. For the primary analyses of follow up at 6, 12 and 24 months, these non-responders will be retained in the ITT analysis as non-responders to their primary assignment at randomization. However, when we perform exploratory analyses of treatment combinations, these subjects will be treated as distinct groups and compared to patients who received monotherapy for the duration of the study. These comparisons (Aim D) are exploratory because there is insufficient power to test for significance. The left column of boxes in Figure 3 shows how we intend to follow up the responders to EMM.

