#### 8.3 Analysis of Secondary Aims

*Identify predictors of treatment response to each intervention.* Generalized linear modeling will be used to identify baseline variables which are significant independent predictors of responder status at 3 months. Candidate independent variables in these models include (a) demographic variables (e.g., sex, age, race, ethnicity, education); (b) clinical history variables (e.g., FI frequency, volume, duration, and association with urgency and diarrhea); and (c) baseline pelvic floor physiology (e.g., anal canal resting pressure, squeeze pressure, duration of squeeze, rectal sensory threshold for first sensation and urgency, maximum tolerable volume, structural integrity of anal sphincters assessed by ultrasound, and integrity of the pelvic floor innervation by trans-sacral and trans-lumbar magnetic evoked potentials) and other moderator variables described in the protocol. Differences in predictors of response among the treatment groups will be assessed by evaluating interaction terms for the predictors and treatment group. Secondary analyses evaluating predictors of treatment response at other time points and predictors of other secondary outcomes will be conducted using similar methods.

Investigate the mechanistic basis for treatment success for each intervention. General linear modeling will be used to identify measures associated with change from baseline to 3 months in FI frequency. The independent variables to be tested are anal squeeze pressures, rectal sensory thresholds, rectal maximum tolerable volume, trans-lumbar and trans-anal magnetic evoked potential, stool consistency measure by the Bristol Stool Form Scale, and adherence to protocol. Differences in predictors among the treatment groups will be assessed by evaluating interaction terms for the predictors and treatment group.

*Evaluate treatment combinations.* To assess the effectiveness of allowing non-responders to choose an additional treatment at 3 months, we will estimate 95% confidence intervals for the number of responders in each treatment-order combination at 6, 12, and 24 months using a Wilson Score interval. Confidence intervals will be compared descriptively.

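### Aim D compares add-on treatments that 3-month non-responders choose for themselves, but the responder-rate comparison is unadjusted, so a gap between SNS and the other add-on cannot be separated from who chose which

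*Combined protocol and SAP*

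**What the plan says.** **Allocation of the add-on.** Section 3.0, item 4, says of patients short of a 75% reduction at 3 months that "they will be invited to choose either the treatment to which they were not randomized or SNS as an adjunctive treatment". Section 2.3 adds a clinical filter on SNS, saying that patients "who do not meet clinical criteria for receiving SNS, or who previously received and did not respond to SNS treatment will not be offered" this option.

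**Objective.** In Section 1.1, objective 4 plans to "compare improvement among various treatment combinations, up to 24 months after administration of each treatment combination, compared to monotherapy", and Aim D states that "differences in responder rates between groups will be assessed". Objective 5 asks for differences between combinations in the size of the improvement.

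**Analysis.** Under the evaluation of treatment combinations, Section 8.3 says "we will estimate 95% confidence intervals for the number of responders in each treatment-order combination at 6, 12, and 24 months", using the Wilson score method, and then "Confidence intervals will be compared descriptively". No covariate is named. Section 8.2 separately plans a longitudinal model of change in FISS, with estimates for each group of non-responders by the combination they chose, and applies the same method to FIQOL and the PROMIS scales. Its listed terms are randomized treatment, site, sex, time and treatment by time.

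**Status.** Section 5.4 says: "These comparisons (Aim D) are exploratory because there is insufficient power to test for significance".

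**The concern.** A responder has at least a 75% reduction from the diary kept before EMM (Section 4.1.1). Non-responders therefore reach the add-on at different distances from the same threshold. A patient already 60% below baseline has 40% left and must reach 25%, a further reduction of 1 − 25/40 = 37.5%. A patient who has not improved needs 75%. If that distance also affects whether the patient picks SNS, the two add-on groups differ in prognosis before the add-on starts.

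The feasibility survey in Section 5.5 shows that patients do not see the options as interchangeable. Respondents were more willing to try BIO than INJ and INJ than SNS, and rated SNS the least safe. Aim D is meant to supply preliminary data for a later study, and a selection artefact could mislead that study about which add-on is worth testing.

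**Working it through.** **1. The plan's own figures reproduce.** The Wilson interval at 50% is 33.2–66.8% for n = 30 (Table 8: 33–67%) and 35.2–64.8% for n = 40 (Table 8: 35–65%). All 27 cells of Table 8 agree within one point. The choosers in Section 5.4 follow from 63 INJ and 17 BIO non-responders with an even split: (63 + 17)/2 = 40 for SNS, 63/2 = 31.5 (stated 32) for BIO, and 17/2 = 8.5 (stated 9) for INJ.

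**2. The likely confounder is recorded before the choice takes effect.** The measurements table schedules the diary and FISS at 3 months. Section 3.1 has the optional treatment starting 0 days to 4 weeks after that visit.

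**3. How large a gap can selection alone produce?** Take INJ non-responders and assume that SNS and added BIO work equally well.

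- From Table 3, 53% of INJ patients reached a 50% reduction and 32% reached 75%. The share of non-responders already at 50–74% (call them near) is s = (53 − 32)/(100 − 32) = 21/68 = 0.309. Section 2.2.2 shows the 53% to be a six-month result of another trial, so carrying s over to this trial is an assumption.
- Let a and b be the chances that near and far patients choose SNS. Assume half choose SNS overall, s·a + (1 − s)·b = 0.5, and that far patients have OR times the odds of choosing it, [b/(1 − b)]/[a/(1 − a)] = OR. The values of OR are assumed.
- The near share is s·a/0.5 among SNS choosers and s·(1 − a)/0.5 among BIO choosers. For OR = 2, a = 0.382 and b = 0.553, giving 0.236 and 0.382.
- Apparent gap = (difference in near share) × (response in near − response in far).

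The four right-hand columns give the gap in points for assumed near versus far response rates.

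| OR | Near share, SNS / BIO choosers | Difference | 100% v 0% | 70% v 20% | 60% v 30% | 60% v 40% |
|---|---|---|---|---|---|---|
| 2 | 23.6% / 38.2% | 14.6 | 14.6 | 7.3 | 4.4 | 2.9 |
| 3 | 19.6% / 42.2% | 22.6 | 22.6 | 11.3 | 6.8 | 4.5 |
| 4 | 16.9% / 44.9% | 28.0 | 28.0 | 14.0 | 8.4 | 5.6 |

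The 100% v 0% column is what follows if each add-on exactly halves the remaining FI: only patients at 50–74% then cross the threshold. It is the largest separation possible. The other columns are softer illustrations. Here SNS looks worse; if near patients favoured SNS, the sign would reverse.

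**4. Sampling error against bias.** With 32 v 31 patients and both groups at 50%, the Newcombe 95% interval for the difference is about ±23 points; with 9 v 8 (BIO arm) it is about ±39. Power for 40% v 60% is about 35% at 31 per group and 12% at 8. The statement in Section 5.4 about power is therefore right. But the gap formula in step 3 contains no sample size: more patients would narrow the interval around a biased contrast.

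**The case against.** The strongest reply is that choice is part of what Aim D studies. Section 8.3 introduces the analysis as judging the value of letting non-responders choose, and Sections 1.1, 3.0 and 5.3 call the design pragmatic and a reflection of clinical practice. Responder rates among choosers describe that properly. The results are already labelled preliminary or exploratory in several places, and no formal test is planned. This stands for the rate within each group. It does not cover objective 4, which compares combinations with each other, or Aim D's intention to assess differences.

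Three stronger readings are tempting, and the documents do not support them.

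- A reader might infer that raw Wilson intervals are the only analysis by combination, or that the two randomized arms are mixed. Section 8.2 also plans models with site and sex, and treatment-order combinations already separate the arms. What is missing from both analyses is 3-month status.
- A reader might infer that SNS will look 15 to 28 points worse. That needs the 100% v 0% column and choice odds of 2 to 4, for which no source exists. The survey asked about willingness before any study treatment, not about the choices of 3-month non-responders. The 31% share may not transfer either: baseline here precedes EMM, and Section 6.1 reports an average 60% fall in FI during a similar run-in.
- A reader might infer that full covariate adjustment would rescue the comparison. With about 0.309 × 63 ≈ 19 responders in the INJ arm under the halving scenario, and about 45 patients followed to 24 months (Table 7), a model with several covariates is not realistic. Adjustment also cannot repair differences in eligibility for SNS.

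**Conclusion.** The concern holds as a limited, inexpensive improvement. The add-on groups are self-selected, with an extra clinical filter on SNS, and no planned analysis by combination accounts for status at 3 months. A raw difference between SNS and the other add-on is therefore not interpretable as a difference in treatment effect.

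Across the scenarios above, selection alone gives roughly 3 to 28 points, a range that includes the 20-point minimum important difference in Section 5.2.1. Every scenario rests on assumed choice odds, assumed response rates and a share taken from another trial, so the range shows what is possible and predicts nothing. The direction is unknown. Most of these gaps also lie within the sampling error expected in the INJ arm.

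The exploratory label does not settle the matter, because its reason in Section 5.4 is power alone. A reader might extend the point to the main result, but the randomized primary comparison is untouched: it is made at 3 months before any add-on, and in later analyses non-responders keep that status in their assigned arm.

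**What to change.** 1. **Section 5.4:** state that the Aim D comparisons are exploratory and non-causal because the groups are self-selected as well as small.
2. **Section 8.3:** within each randomized arm, tabulate 3-month diary FI frequency, percent reduction from baseline and FISS by chosen add-on, and identify the patients who were not offered SNS.
3. **Section 8.3, INJ arm only:** add a sensitivity analysis of SNS versus added BIO among patients eligible for both, adjusted for 3-month diary FI frequency on the log scale, reporting the adjusted difference with a 95% confidence interval. Keep the BIO arm, with about 8 to 9 per choice, descriptive.

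The cost is analysis-plan wording, one table and one small model. The diary and FISS data are already scheduled, and no visit or treatment changes. The drawbacks are low precision, made worse by restricting to patients eligible for both options, and unmeasured reasons for choice that remain. The adjusted estimate should therefore carry the same non-causal label.

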## 5.3. Secondary Aim to Evaluate Treatment Combinations

A secondary aim of the study is to evaluate treatment-order combinations after participants are allowed to cross over into other study arms. At the 3-month assessment, non-responders to randomized treatment can choose to initiate an additional treatment. This is a pragmatic approach reflecting the reality that patients in clinical care who are not happy with their initial FI treatment may choose to try another treatment. Table 7 shows the number of 3-month non-responders in each randomization group who are expected to be followed to 6, 12 and 24 months with the assumption of 15% attrition (loss to follow up or missing outcomes for other reasons) between the 3- and 12-month assessments and an additional 15% attrition between the 12- and 24-month assessments. Since non-responders can choose to try the other study treatment or SNS after 3 months, we estimate that between 5 and 50 participants will be in each of the possible treatment-order combinations at 6, 12 and 24 months. We will estimate 95% confidence intervals for the number of responders in each treatment-order combinations at 6, 12 and 24 months. We will estimate 95% confidence intervals for the number of responders in each treatment-order combinations at 6, 12 and 24 months. We will estimate 95% confidence intervals for the number of responders in each treatment-order combinations at 6, 12 and 24 months. We will estimate 95% confidence intervals for the number of responders in each treatment-order combination at each time point. Table 8 shows 95% confidence intervals for a range of group sizes and responder percentages; confidence intervals are estimated using a Wilson Score interval recommended for small sample sizes.

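### Research objective 5 asks for differences between treatment combinations in the magnitude of FI improvement, but no planned analysis produces such a difference

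*Combined protocol and SAP*

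**What the plan says.** Section 1.1, Aim D, contains two commitments to a between-group comparison. Research objective 5 is "To estimate differences in the magnitude of improvement in FI from baseline to end of treatment between the treatment combinations". The introductory text of the aim adds that "differences in responder rates between groups will be assessed".

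The matching analysis is in section 8.3 under treatment combinations: "we will estimate 95% confidence intervals for the number of responders in each treatment-order combination at 6, 12, and 24 months", by the Wilson score method, followed by "Confidence intervals will be compared descriptively". Section 5.3 plans the same intervals and gives the scale: "we estimate that between 5 and 50 participants will be in each of the possible treatment-order combinations".

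Section 8.2 is also relevant. For the FISS it plans model-based 95% confidence intervals for change from baseline at 6 to 24 months, with separate estimates for non-responders who choose each combination. FIQOL and the PROMIS scales follow the same methods. These intervals, too, are compared descriptively and without formal testing.

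Section 5.4 labels the Aim D comparisons exploratory because power is insufficient for significance testing.

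**The concern.** Objective 5 needs two things: a magnitude of improvement, and a difference in that magnitude between combinations. Section 8.3 supplies neither for diary FI. It reports, one group at a time, how many patients cross the 75% line. Section 8.2 supplies a magnitude for the FISS and the other scales but stops before the difference.

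A team that follows the plan exactly would finish with sets of separate intervals and no estimate for a numbered objective. Overlap of separate intervals is a poor guide to the size or precision of a difference. Aim D is meant to give preliminary data for a future study, and the designers of that study would need the difference and its interval.

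**Working it through.** **1. Does any planned analysis produce the estimate?**

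| Place | Scale | By combination? | Difference between combinations? |
|---|---|---|---|
| 8.3, treatment combinations (same in 5.3) | 75% responder, yes/no | Yes | No; intervals compared descriptively |
| 8.2, efficacy through 24 months | 75% responder, yes/no | No; 3-month non-responders stay failures | No |
| 8.2, FISS, FIQOL, PROMIS | Continuous score change | Yes | No; intervals compared descriptively |
| 8.2, 50% responder and continence | Yes/no, by the primary-endpoint methods | Not stated | No |
| 8.3, mechanistic model | Change in FI frequency | No; stops at 3 months, before any added treatment | No |
| 1.1, Aim D text | Responder rate | Yes | Promised, but no method in 8.3 |

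No row gives a between-combination difference in magnitude. No row analyses diary frequency by combination after 3 months on its full scale.

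**2. Reproducing the plan's own figures.** The Wilson interval is [p + k²/2n ± k·√(p(1−p)/n + k²/4n²)] / (1 + k²/n), with k = 1.96. For n = 10 and p = 0.50 the centre is (0.50 + 0.192)/1.384 = 0.50. The half-width is 1.96 × √(0.025 + 0.0096)/1.384 = 0.263, giving 24-76% as printed in Table 8. All 27 printed cells of Table 8 reproduce.

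**3. Group sizes.** Section 5.4 expects 63 INJ and 17 BIO non-responders, splitting equally between two options. That is 63/2 = 31.5 (taken as 32 and 31) and 17/2 = 8.5 (taken as 9 and 8). Table 7 has 45 and 13 followed to 24 months, so about 22 and 6 per combination.

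**4. What a difference interval would look like.** The pairs below share the same randomized treatment.
- Responder rates, Newcombe interval, both rates set at 50% (my assumption). The half-width is the root sum of squares of the two Wilson half-widths:
  - 32 versus 31: √(16.4² + 16.6²) ≈ 23 points
  - 9 versus 8: √(27.3² + 28.5²) ≈ 39 points
  - 22 versus 22, about 24 months: √2 × 19.3 ≈ 27 points
  - 6 versus 6, about 24 months: √2 × 31.2 ≈ 44 points
- Difference in mean change, t-interval. The half-width in SD units is t × √(1/n₁ + 1/n₂):
  - 32 versus 31: 2.000 × 0.252 = 0.50 SD
  - 9 versus 8: 2.131 × 0.486 = 1.04 SD
  - 22 versus 22: 2.018 × 0.302 = 0.61 SD
  - 6 versus 6: 2.228 × 0.577 = 1.29 SD

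The documents give no SD of change. If it were 1.5 to 2.1 FI days per week (SDs quoted for other quantities in section 2.2.1 and Table 3), the 3-month group sizes give:
- 32 versus 31: 0.50 × 1.5 to 0.50 × 2.1, about 0.75 to 1.05 days per week
- 9 versus 8: 1.04 × 1.5 to 1.04 × 2.1, about 1.6 to 2.2 days per week

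**The case against.** **The plan already covers much of this.** Section 8.2 does give continuous change by combination, and objective 5 speaks of improvement in FI without naming the diary. The FISS is a continuous FI severity scale covering frequency, type and volume of leakage. This stands, and it rules out saying that the plan offers nothing but responder counts. It does not close the gap. The FISS is a past-month composite rather than the diary frequency that defines response in this trial, and its between-combination difference is not planned either.

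**Aim D is declared exploratory and underpowered.** True, and it limits the importance of the point. But section 5.4 speaks of testing, while objective 5 asks for estimation. Low power is no reason to leave the estimate out.

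**Two stronger readings are tempting and not supported.**

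A reader might infer that the diary data are thrown away. They are collected and entered in the EDC at 3, 6, 12 and 24 months; for this purpose they are only unused.

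A reader might also infer that the full scale would give clearly more power than the 75% cut. Under a normal model the cut keeps about 64% of the information at a 50% response rate and 49% at 80%. With 32 versus 31 patients and Table 1 rates of 78% (BIO) and 56% (SNS), power is 48% for a z-test on responders (43% for Fisher) and 68% for a t-test on an underlying normal scale. But Table 1 also gives continence of 44% for BIO and 40% for SNS, so many ratios would be zero and normality fails. Simulations that used those figures, the documents' 50%-response rates, and values spread evenly within each band (an assumption) gave a rank test on the full scale about 20-28% power, or 49-58% with Table 1's lower SNS continence figure of 25%. The direction of any gain is therefore not established.

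**Conclusion.** The point holds as a mismatch between a numbered objective and its analysis: followed as written, the plan does not produce the difference that objective 5 asks for, on the diary scale or any other. That conclusion rests on the text alone.

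Its weight is modest. It affects an exploratory aim in self-selected groups of about 8 to 32 patients, and no primary conclusion depends on it. Supplying the estimate would make the objective answerable and show its imprecision openly; it would not make the comparison precise or causal. The half-widths assume the section 5.4 split, equal 50% response rates and, for the continuous scale, a common SD with approximate normality. For skewed diary counts they are indicative only. No power gain is claimed.

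**What to change.** In section 8.3, under treatment combinations:

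1. Add an exploratory analysis, labelled non-randomized, of weekly diary FI frequency at 6, 12 and 24 months by treatment-order combination. Use a count model that accommodates zeros, such as a negative binomial with baseline frequency as offset or covariate. Eligibility requires at least two episodes per week at baseline, so the log of baseline is defined. A log-ratio of each patient's own counts is not suitable, because it is undefined for continent patients.
2. For groups of about 8-9, where such a model is fragile, use a bootstrap interval for the difference in mean or median change.
3. Report differences or rate ratios from baseline, with 95% CIs, between combinations that share the same randomized treatment.
4. Add the matching FISS differences, and Newcombe intervals for the responder-rate differences that Aim D promises.
5. State which assessment counts as end of treatment for a combination.
6. Keep the Wilson intervals.

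Do not use the ratio to the 3-month diary as a main measure. Patients enter these groups because of that diary, so the ratio invites regression to the mean, and objective 5 is defined from baseline.

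The cost is SAP wording, one further exploratory model on data already collected, a distributional assumption for skewed counts, and a few tables whose intervals will be wide. If the team does not want this analysis, objective 5 should be reworded to match section 8.3.
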